4.3. Secondary Endpoints Analyses

4.3.1. Definition of endpoints/estimands

Refer to Section 1.1 for the definition of secondary safety and immunogenicity (humoral and CCI) endpoints/estimands.

4.3.2. Main analytical approach

4.3.2.1. Safety analysis

The estimand analysis for safety will be performed on the ES for participants in Part A and Part B. For the analysis of solicited events, the daily assessment from the investigator (either to correct the participant entry or to replace a missing participant entry) will take precedence over the participant's entry only when the investigator assessment is done up to 36 hours after 23h59 of the specified day.

Descriptive analysis by group will be summarized as follows:

- The safety follow-up time will be tabulated using descriptive statistics (mean, median, minimum, maximum), including the percentage of participants with at least 6 months safety follow-up post-vaccination.
- The number and percentage of participants with at least one administration site event (solicited and unsolicited), with at least one systemic event (solicited and unsolicited) and with any AE (solicited and unsolicited) during the 4-day and the 30-day follow-up period after vaccination will be tabulated with exact 95% CI. The same computations will be done for Grade 3 AEs, for Grade 3 non-serious AEs and for AEs resulting in a medically attended visit. Those analyses will present all solicited and unsolicited AEs, including SAEs (unless otherwise specified).
- The number and percentage of participants with at least one administration site event (solicited only), with at least one systemic event (solicited only) and with any solicited event during the 4-day follow-up period (i.e., the day of study intervention administration and 3 subsequent days) after vaccination will be tabulated with exact 95% CI. The same computations will be done for Grade 3 AEs and for AEs resulting in a medically attended visit.
- Compliance in completing solicited events information will be tabulated (See Section [6.2.2](#)).
- The number and percentage of participants reporting each individual solicited administration site or systemic event (any grade, Grade 3 and resulting in medically attended visit) during the 4-day follow-up period after vaccination will be tabulated with exact 95% CI. If the proportion of participants who completed the eDiary entries from Day 1 through Day 4 is below 90%, the outputs will also be tabulated for these participants only (see Section [6.2.2](#)).
- For fever, the number and percentage of participants reporting fever by half degree (°C) cumulative increments during the 4-day follow-up period after vaccination will be tabulated.
- The percentage of participants with each solicited administration site event and solicited systemic event (any grade and Grade 3) during the 4-day follow-up period after vaccination will be represented graphically.
- The duration in days of each individual solicited event will be tabulated using descriptive statistics (mean, min, Q1, median, Q3, maximum). The same computations will be done for the number of days with Grade 3 solicited events. The duration will be calculated for both definitions in Section [6.3.3.9](#) and the outputs will be tabulated for all participants and for the participants from Cohort 3 enrolled as of 8August24, as from then the eDiary alerts for participants from Day 5 onwards were activated in the vendor system.
- The number and percentage of participants with any unsolicited AEs during the 30-day follow-up period (i.e., the day of vaccination and 29 subsequent days) with its exact 95% CI will be tabulated by group and by MedDRA Primary System Organ Class (SOC), High Level Term (HLT) and Preferred Term (PT). Similar tabulation will be done for Grade 3 unsolicited AEs, for any causally related unsolicited AEs,

for Grade 3 causally related unsolicited AEs and for unsolicited AEs resulting in a medically attended visit. The analyses of unsolicited AEs will include SAEs and AESIs (i.e. pIMDs and AF).

- The number and percentage of participants with any non-serious unsolicited AEs during the 30-day follow-up period (i.e., the day of vaccination and 29 subsequent days) with its exact 95% CI will be tabulated by group and by MedDRA Primary SOC, HLT and PT. Similar tabulation will be done for Grade 3 non-serious unsolicited AEs, for any causally related non-serious unsolicited AEs, for Grade 3 causally related non-serious unsolicited AEs and for non-serious unsolicited AEs resulting in a medically attended visit.
- The number and percentage of participants with any unsolicited AEs reported within 30 minutes following vaccination with its exact 95% CI will be tabulated by group and by MedDRA Primary SOC, HLT and PT. Similar tabulation will be done for Grade 3 unsolicited AEs reported within 30 minutes following vaccination.
- The verbatim reports of unsolicited AEs, including SAE and AESI, will be reviewed by a qualified person and the signs and symptoms will be coded according to the MedDRA Dictionary for Adverse Reaction Terminology. Every verbatim term will be matched with the appropriate Preferred Term.
- The number and percentage of participants with at least one report of SAE classified by the MedDRA Primary SOC, HLT and PT from vaccination up to study end (6 months after study intervention administration) will be tabulated with exact 95% CI.
- The number and percentage of participants with at least one report of SAE classified by the MedDRA Primary SOC, HLT and PT, related to study intervention administration, from vaccination up to study end (6 months after study intervention administration) will be tabulated with exact 95% CI.
- The number and percentage of participants with any fatal SAE, from vaccination up to study end (6 months after study intervention administration) will be tabulated with exact 95% CI.
- The number and percentage of participants with at least one report of pIMD classified by the MedDRA Primary SOC, HLT and PT from vaccination up to study end (6 months after study intervention administration) will be tabulated with exact 95% CI.
- The number and percentage of participants with at least one report of pIMD classified by the MedDRA Primary SOC, HLT and PT, related to study intervention administration, from vaccination up to study end (6 months after study intervention administration) will be tabulated with exact 95% CI.
- All SAEs, pIMDs and AFs from vaccination up to study end (6 months after study intervention administration) will also be described in detail in a tabular listing.
- AEs/SAEs leading to study discontinuation from vaccination up to study end (6 months after study intervention administration) will be tabulated.

- For web posting purposes, the number of occurrences and the number and percentage of participants with non-serious AEs (solicited and unsolicited combined) during the 30-day follow-up period will be produced by SOC and PT.
- In case of pregnancies, these will be described in detail in a tabular listing.
- AF AESIs will be tabulated within the summary of AEs or SAEs according to their classification.

Refer to Section 6.1.5 and Section 6.1.6 for the analysis of concomitant medications and concomitant vaccination.

4.3.2.2. Immunogenicity analysis: humoral immune response

The estimand analysis for immunogenicity will be performed on the PPS for participants in Part A. If, in any group, the percentage of vaccinated participants with serological results excluded from the PPS is more than 5%, a second analysis based on the ES will be performed to complement the PPS analysis.

4.3.2.2.1. Between groups assessment

Considering the sampling timepoint at 1-month post-study intervention administration, same analysis as for primary endpoint (refer to Section 4.2.2) will be performed using **CCI** unit for computation of the GMT ratio and SRR difference.

Considering the sampling timepoint at 6-month post-study intervention administration, the following analysis will be performed:

- The 95% CIs for group GMT ratios (RSV-OA (≥ 60 YOA) cohort over RSV-A-AIR (18-49 YOA) cohort) will be derived from an ANCOVA model on \log_{10} -transformed titers for each neutralization assay. The model will include the group and the baseline \log_{10} -transformed titer as covariate. The group GMT ratios will be based on a back transformation of group contrast in the ANCOVA model applied to the logarithmically transformed titers.
- The 95% CIs for group SRR difference (RSV-OA (≥ 60 YOA) cohort minus RSV-A-AIR (18-49 YOA) cohort)
- Results will be reported using both ED60 and **CCI** units.

All between groups analyses of secondary endpoints presented in this section will be descriptive with the aim to characterize the difference in immunogenicity between groups. These descriptive analyses should be interpreted with caution considering that there is no adjustment for multiplicity for these comparisons.

4.3.2.2.2. *Within groups assessment*

For each timepoint with blood sample collection for humoral immune response and for RSV-A/B neutralizing titers, the following analysis will be performed by group:

- a. Percentage of participants with neutralizing titers equal to or above pre-defined assay cut-offs and their 2-sided 95% CIs will be tabulated.
- b. SRR and 95% CI will be tabulated.
- c. Unadjusted GMTs and their 95% CIs will be tabulated and displayed graphically.
- d. The kinetics of unadjusted GMTs will be plotted as a function of time for participants with results available at all timepoints.
- e. MGIs and their 95% CIs will be tabulated.
- f. Distribution of neutralizing titers will be displayed using reverse cumulative curves.
- g. Results will be reported using both ED60 and CCI units.

[figure not shown]
4.3.3. *Additional considerations*

4.3.3.1. *Atrial Fibrillation (AF) AESIs*

Potential AF AESIs will be identified through the MedDRA preferred term of interest atrial fibrillation (10003658). Sites will be prompted via query to complete any necessary additional information for these AESIs in the eCRF. Additional analysis might be performed on those additional data collected for AF AESIs.

AF AESIs will be described in a tabular summary including the characteristics of the AE (seriousness, causality, maximum intensity), time to onset and outcome.

[figure not shown]
4.4. *Tertiary Endpoint Analyses*

CONFIDENTIAL

222253

CCI

CCI

4.5. Other Safety Analyses

Not applicable.

4.6. Other Analyses

4.6.1. Subgroup analyses

4.6.1.1. Immunogenicity analysis by age at vaccination

As exploratory analysis, the descriptive within group immunogenicity analysis (humoral results) points a, b, c, e (except the graphical displays) and g described in Section 4.3.2.2.2 will also be generated by age at vaccination: 18-49 YOA, 60-69 YOA and ≥ 70 YOA.

CCI

4.7. Interim Analyses

4.7.1. Sequence of analysis

The analyses will be performed stepwise:

- **Day 31 (Part A):** A first analysis will be performed on all immunogenicity, reactogenicity and safety data available and as clean as possible, when data for at least primary and secondary endpoints up to Visit 2 (Day 31) are available for all participants in Part A. This analysis will be considered as final for the primary endpoints.
- **Month 6 (Part A):** If required, a safety analysis can be performed when safety data up to Month 6 are available and as clean as possible, for all participants in Part A.
- **Day 31 (Part B):** If required, a safety analysis can be performed when safety data up to Visit 2 (Day 31) are available and as clean as possible, for all participants in Part B. This analysis may be combined with Month 6 safety analysis for Part A.
- **Month 6 (Part A):** If required an immunogenicity analysis can be performed when all data for secondary endpoints up to study conclusion (Visit 3, Month 6) are available and as clean as possible, for all participants in Part A.

- An **EOS** analysis will be performed when all immunogenicity and safety data up to study conclusion (Visit 3/Contact, Month 6) will be available for all participants in Part A and Part B.
- If the data of different analyses become available around the same timepoint, these analyses can be combined into one analysis.

4.7.2. Statistical considerations for interim analysis

No statistical adjustment for interim analysis is required.

4.8. Changes to Protocol Defined Analyses

There were no changes or deviations to the originally planned statistical analysis specified in the protocol (Dated: 18 Dec 2023).

5. SAMPLE SIZE DETERMINATION

The target sample size for the study is approximately 850 participants: 425 participants in Cohort 1 (RSV-A-AIR [18-49 YOA group]) and 425 participants in Cohort 2 (RSV-OA [≥ 60 YOA group]), to obtain at least 722 evaluable participants (361 participants in the RSV-A-AIR [18-49 YOA] cohort and 361 participants in the RSV-OA [≥ 60 YOA] cohort) for the evaluation of the primary objectives, assuming that approximately 15% of the enrolled participants will not be evaluable.

Participants who withdraw from the study will not be replaced.

The power to demonstrate the primary NI objectives following the hierarchical testing procedure described in Section 2.1 is presented in [Table 6](#).

Table 6 Power for primary objectives of non-inferiority of the humoral immune response after RSVPreF3 OA vaccine between the RSV-A-AIR (18-49 YOA) Cohort 1 to RSV-OA (≥ 60 YOA) Cohort 2 for 361 evaluable participants per group

Objective	Standard deviation (SD) of log10 titers / SRR (%)	Non-inferiority margin	Type II Error	Power ¹
NI for RSV-A strain				
GMT RSV-A	SD=0.45	1.5	0.05	99.95%
SRR RSV-A	SRR=81.6% ²	10%	6.92	93.08%
Global power for RSV-A strain				93%
NI for RSV-B strain				
GMT RSV-B	SD=0.45	1.5	0.05	99.95%
SRR RSV-B	SRR=78.7% ²	10%	9.56	90.44%
If non-inferiority is demonstrated for RSV-A, global power for RSV-B strain				90%

NI=Non-inferiority; SRR=Seroresponse rate; GMT=Geometric mean titer; RSV=Respiratory syncytial virus

¹Pass 2019 1-sided alpha=2.5% for each endpoint (GMT ratio and SRR difference), two-Sample T-Tests for Non-Inferiority assuming equal variance for group GMT ratios and Miettinen and Nurminen for Non-Inferiority tests for group SRR difference, Non-inferiority limit=0.176 (=log10(1.5)) for group GMT ratios

²Reference from RSV OA=ADJ-006

For the evaluation of reactogenicity and safety, the sample size of 1025 participants in combined Cohorts 1 and 3 (RSV-A-AIR group) has 64% and 87% probability of observing at least one vaccinated participant with AE if the true AE incidence rate is 0.1% and 0.2% respectively. This probability increases to at least 95% for true AE incidence rates $\geq 0.3\%$.

6. SUPPORTING DOCUMENTATION

6.1. Appendix 1 Study Population Analyses

6.1.1. Participant Disposition

A summary of the number and percentage of participants who completed the study as well as those who prematurely withdrew from the study will be provided. Reasons for study withdrawal will be summarized. This analysis will be based on the Screened set, Enrolled set, ES.

6.1.2. Demographic and Baseline Characteristics

Demographic and baseline characteristics (age at vaccination in years, sex, race, ethnicity, country, vital signs, Body Mass Index (BMI) and smoking status) will be summarized by group using descriptive statistics. This analysis will be based on the ES, PPS and on the CCI subset of the ES and PPS for all the parameters except vital signs. The vital signs will be summarized based on the ES. If the summary of demographic characteristics for public disclosure meets the criteria for de-identification, as described in the relevant procedural document, a de-identified version will be produced.

The following age categories will be considered in the analysis: 18-49 YOA, 60-69 YOA, ≥ 70 YOA and ≥ 80 YOA. In addition, for web posting purposes: 18-64 YOA, 65-84 YOA and ≥ 85 YOA.

The number and percentages of participants with medical history classified by the MedDRA Primary SOC, HLT and PTs will be tabulated by group for the ES. The same tabulation will be done for the ongoing baseline chronic diseases of interest.

6.1.3. Protocol Deviations

Protocol deviations will be tracked by the study team throughout the conduct of the study. These protocol deviations will be reviewed to identify those considered as important as follows:

- Data will be reviewed prior to freezing the database to ensure all important deviations (where possible without knowing the study intervention details) are captured and categorised in the protocol deviations dataset and all deviations leading to exclusions from analysis sets are captured.
- This dataset will be the basis for the summaries of important protocol deviations.

A summary of important protocol deviations will be provided by group, based on the Screened set.

The number of participants screened for the study as well as the number of participants excluded from the Enrolled set, ES and the PPS analyses will be tabulated. These will be based on the Screened set, Enrolled Set and the ES, respectively.

6.1.4. Participant exposure

The number and percentage of participants who received the study intervention will be tabulated by group for the ES.

6.1.5. Prior and Concomitant Medications

Concomitant medications will be coded using the WHO Drug dictionary.

The number and percentage of participants using concomitant medication (any medication, any antipyretic and any antipyretic taken prophylactically) during the 4-day and the 30-day follow-up period after vaccination will be tabulated with exact 95% CI per study group for the ES.

6.1.6. Concomitant Vaccinations

The number and percentage of participants and doses with concomitant vaccination during the 30-day follow-up period will be tabulated with exact 95% CI per study group for the ES.

6.2. Appendix 2 Electronic Clinical Outcome Assessment (eCOA) Compliance

6.2.1. Study Level compliance

An eDiary will be used in this study to capture solicited administration site or systemic events. All solicited events that occur during the four days following administration of the dose of the study intervention (Day 1 to Day 4) must be recorded into the eDiary, irrespective of intensity. An automatic reminder to complete the eDiary will be sent to the participants during this time frame. Daily eDiary compliance will be checked by the investigator or delegate on the eDiary portal. In case of non-compliance, the investigator should contact the participant within 36 hours to remind the importance of daily entries. After review and verbal discussion of the eDiary entries with the participant, if there are clear eDiary errors/omissions the investigator will complete his/her own assessment within 36 hours in the relevant sections of the eCRF.

During the enrolment period a review of the eDiary compliance during the 4-day follow-up period will be conducted by the central monitoring team for follow-up with the sites if needed.

eCOA compliance for *each day* of the 4-day follow-up period is defined as:

$$\frac{\text{Number of participants with the eDiary completed for the corresponding day}}{\text{Expected number of participants with the eDiary completed for the corresponding day}}$$

eCOA compliance for the overall 4-day follow-up period is defined as:

$$\frac{\text{Number of participants with the eDiary completed}}{\text{Expected number of participants with the eDiary completed}}$$

The above eCOA compliance will be calculated using the participant entries, with Quality Tolerance Limits (QTLs) defined as: 90% (action limit), 75% (critical limit)

6.2.2. Endpoint Level Compliance

In terms of compliance for each of Days 1-4, the number/percentage of completed eDiaries will be summarized by group and by day, using a frequency table. For each day, the numerator will be the number of participants who completed the eDiary on the specific day and the denominator will be the number of expected completed eDiaries on the specific day (i.e., the number of participants). An overall compliance for Day 1 to Day 4 will also be summarized. The numerator will be the sum of each numerator and the denominator will be the sum of each denominator from the daily compliance. In addition,

the compliance on the 4 consecutive days (Day 1 to Day 4) will be summarized. The numerator will be the number of participants who completed the 4 eDiaries for Day 1 to Day 4. The denominator will be the number of participants. If this compliance on the 4 consecutive days is less than 90%, a sensitivity analysis which includes only participants who completed the 4 eDiaries for Day 1 to Day 4 will be performed for the analysis of incidence of solicited administration site and systemic events within the 4-day follow-up period after vaccination.

For compliance of each day from Day 1 onwards, the number/percentage of completed eDiaries will be summarized by group and by symptom, using a frequency table. The denominator for each symptom will be the number of expected completed diaries (i.e., the number of symptom days from Day 1 onwards) and the numerator will be the number of symptom diaries completed for these expected symptom days. This will be summarized for all participants and for the participants from Cohort 3 enrolled as of 8August24, as from then the eDiary alerts for participants from Day 5 onwards were activated in the vendor system.

For compliance of each day from Day 5 onwards, the number/percentage of completed eDiaries will be summarized by group and by symptom, using a frequency table. The denominator for each symptom will be the number of expected completed diaries (i.e., the number of symptom days from Day 5 onwards) and the numerator will be the number of symptom diaries completed for these expected symptom days. This will be summarized for all participants and for the participants from Cohort 3 enrolled as of 8August24, as from then the eDiary alerts for participants from Day 5 onwards were activated in the vendor system.

For the above summaries, the daily assessment from the investigator (either to correct the participant entry or to replace a missing participant entry) will take precedence over the participant's entry only when the investigator assessment is done up to 36 hours after 23h59 of the specified day.

The number/percentage of daily assessments from the investigator/delegate within 36 hours will be summarized by group and by symptom using a frequency table. The denominator for each symptom will be the number of entries (by either the participant or investigator within 36 hours).

The reasons for investigator/delegate assessment will also be summarized by group and by symptom using a frequency table.

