SAP Amendment 4	15 Jan 2025	Amendment 1: 03 May 2024	Changes for duration of events (Section 6.3.3.9) and	To include additional analyses on duration of

SAP Version	Approval Date	Protocol Version (Date) on which SAP is Based	Change	Rationale
			Endpoint level compliance (Section 6.2.2)	solicited adverse events and eDiary compliance to account for missing eDiary data as of day 5 onwards, due to non-activation of the eDiary alerts for participants from day 5 onwards in the vendor system.

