6.3.3.9. Duration of events

The duration of an event with a start and end date will be the difference between the start and end date plus one day, i.e., an event that starts on 03MAR2018 and ends on 12MAR2018 has a duration of 10 days.

For solicited administration site and systemic events:

- The duration of a solicited AE with at least one day Grade > 0 is defined as End date – Start date + 1, with Start date defined as the first day with the symptom and End date defined as the last day with the symptom in or beyond the solicited period, considering the investigator assessment within 36h and the intensity of the symptom.
- A missing start date will be imputed with the vaccination date.
- The number of days with grade 3 solicited symptom will be defined considering each day with a known grading=3, irrespective of whether the days are consecutive.

To account for missing eDiary data as of day 5 onwards (due to non-activation of the eDiary alerts for participants from day 5 onwards in the vendor system), a sensitivity analysis will be performed using the below definition of duration:

- The duration of a solicited AE with at least one day Grade > 0 is defined as End date – Start date + 1, with Start date defined as the first day with the symptom and End date defined as the day before the first occurrence of the symptom (in or beyond the solicited period) equals ‘N’ with no days having occurrence ‘Y’ afterwards.
- A missing start date will be imputed with the vaccination date.
- If a solicited event is still not reported as ‘N’ at day 30, the end date will be considered equal to vaccination date + 29 days.

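### Does SAP 6.2.2 need a definition of a symptom day before its eDiary compliance tables can be used?

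*SAP*

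**What the plan says.** SAP Section 6.2.2 describes several compliance summaries.

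- **Days 1-4, by group and day.** Here "the denominator will be the number of expected completed eDiaries on the specific day (i.e., the number of participants"). The same section adds a measure over the four consecutive days, also per participant, which triggers a sensitivity analysis of solicited-event incidence if it falls below 90%.
- **Day 1 onwards, by group and symptom.** The denominator is "the number of expected completed diaries (i.e., the number of symptom days from Day 1 onwards").
- **Day 5 onwards, by group and symptom.** The denominator is "the number of expected completed diaries (i.e., the number of symptom days from Day 5 onwards").

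For both by-symptom tables, "the numerator will be the number of symptom diaries completed for these expected symptom days". An investigator assessment made within the 36-hour limit can stand in for a missing participant entry. Nothing is said about a day with neither.

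Section 6.3.3.9 has two end-date rules for the duration of a solicited event. The main rule has "End date defined as the last day with the symptom in or beyond the solicited period". The sensitivity rule ends the event on the day before the first 'N' that has no later 'Y'. If no 'N' is reported by Day 30, "the end date will be considered equal to vaccination date + 29 days". Section 4.3.2.1 uses both: "The duration will be calculated for both definitions in Section" 6.3.3.9, with tables for all participants and for Cohort 3 participants enrolled from 8 August 2024.

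The version history for SAP Amendment 4 says the additions concern "solicited adverse events and eDiary compliance to account for missing eDiary data as of day 5 onwards", because participant alerts from Day 5 had not been switched on.

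**The concern.** A compliance rate is only as clear as its count of what was expected. Here that count is symptom days, and whether the symptom was present is exactly what is unknown when no diary was completed. Section 6.2.2 borrows no rule to settle it, although 6.3.3.9 holds two that would give different answers.

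At stake is what the Day 5 table can show. It was added because entries from Day 5 were being lost. If expected days stop at the last recorded symptom, a participant who stopped entering while still symptomatic adds no missed day. Compliance could then look high with or without alerts. If expected days run to the first 'N', a participant who recovered and never entered 'N' counts as missing up to Day 30.

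A related worry is that Section 6.2.2 measures Days 1-4 against participants in one table and against symptom days in another, so a participant with no entries is counted in one and absent from the other.

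**Working it through.** **The plan's own figure.** The SAP states no percentage for these tables. The one worked figure on the point is the duration example in Section 6.3.3.9: 03 March to 12 March 2018, end minus start plus one = 12 - 3 + 1 = 10 days. It reproduces.

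**Inputs.** The day of dose is Day 1 (SAP 6.3.3.8), so vaccination date + 29 days is Day 30. Expected days run from the start date to the end date, cut at Day 1 or Day 5. Completed days are the expected days that have an entry. A third reading counts only days on which the symptom was recorded.

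**Test records** (completed/expected; every record has 'Y' on Days 1-4):

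| Later entries | Table from | Recorded days only | Main rule | Sensitivity rule |
|---|---|---|---|---|
| None | Day 1 | 4/4 | 4/4 | 4/30 |
| None | Day 5 | 0/0 | 0/0 | 0/26 |
| None on Days 5-9, 'N' Day 10 | Day 1 | 4/4 | 4/4 | 4/9 |
| None on Days 5-9, 'N' Day 10 | Day 5 | 0/0 | 0/0 | 0/5 |
| None on Days 5-6, 'Y' Day 7, 'N' Day 8 | Day 1 | 5/5 | 5/7 | 5/7 |
| None on Days 5-6, 'Y' Day 7, 'N' Day 8 | Day 5 | 1/1 | 1/3 | 1/3 |
| 'N' Day 5 | Day 1 | 4/4 | 4/4 | 4/4 |
| 'N' Day 5 | Day 5 | 0/0 | 0/0 | 0/0 |

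For the first record the sensitivity rule gives 30 - 5 + 1 = 26 expected days from Day 5, and 4/30 = 13.3% from Day 1. The two end-date rules part only when entries are missing after the last 'Y'.

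**Pooled illustration, with assumed shares.** Take 100 participants with 'Y' on Days 1-4. A share m enters nothing later and the rest enter 'N' on Day 5. From Day 1 the main rule gives 400/400 = 100% whatever m is. The sensitivity rule gives 400/(400 + 100 x m x 26):

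- m = 5%: 400/530 = 75.5%
- m = 10%: 400/660 = 60.6%
- m = 20%: 400/920 = 43.5%
- m = 40%: 400/1440 = 27.8%

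So the reading can matter to the printed percentage.

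**What depends on that percentage.**

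- Solicited-event endpoints (SAP 1.1) concern onset within 4 days. Neither duration nor compliance after Day 4 is an endpoint.
- The 90% trigger (4.3.2.1, 6.2.2) and the 90% and 75% quality limits (6.2.1) apply to the 4-day period, not to symptom days.
- Duration is tabulated under both rules. For the first record a reader sees 4 days under one and 30 under the other, whatever 6.2.2 uses.
- The primary analysis rests on neutralizing titers.

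**The case for a change.** The strongest case for a change is that the tables exist to expose lost entries, two of the three readings cannot show a trailing gap, and one sentence would settle it. The first two parts are right. Section 6.2.2 leaves the term undefined, and the material in Section 6.3.2.3 that is deferred to the ADaM specifications covers only whether to use an investigator assessment when dates or times are incomplete.

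The three readings are not equally open, however. If only recorded days counted, numerator and denominator would be equal by construction and the table would carry no information; the numerator wording presupposes that some expected diaries are absent. The main rule would leave unseen the very gap the amendment was written for. Amendment 4 lists 6.2.2 and 6.3.3.9 under one rationale, and the sensitivity rule opens with that same rationale. An analyst is therefore led to count until 'N', or to show both rules as for duration. This is inference from context, not stated text. When a diary was due after Day 4 may also be set out in the eDiary Manual or the completion guidelines, which the documents mention but do not include.

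The point about Days 1-4 does not stand. One table is by day with participants as its base; the other is by symptom with symptom days as its base. They are openly different measures. A participant with no entries is 0/4 in the first, and so is already counted as non-compliant there.

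**Conclusion.** No change to the plan is needed. The gap is real but is missing programming detail in descriptive tables, of the kind analysts fill when they write table specifications. For a record that stops after Day 4 with the symptom present, the span is 4/4 against 4/30 from Day 1 and 0/0 against 0/26 from Day 5. The effect on a pooled cell cannot be sized, because the documents do not give the frequency of such records; the shares in the illustration are assumed.

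Naming a rule would not make the table clean. One rule leaves trailing gaps uncounted, and the other treats unreported recovery as missing diaries. The plan already brackets this uncertainty where it matters, by reporting duration under both rules and separately for participants enrolled after the alerts were activated.

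The conclusion assumes that the compliance tables stay descriptive and that the rule used is evident from the table or its programming specification. No result on Day 1-4 incidence, no trigger and no non-inferiority conclusion can move with the choice.
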